This is a study where patients will be randomized to two groups. One group will receive Local anesthetic and Tenex. The second group will receive local anesthetic only. The second group will be given the option of crossing over to local anesthetic and Tenex group at 1-month visit. Please note Local anesthetic is standard of care for diagnostic purposes. Both groups will be receiving the same anesthetic.

Subjects shoulder ROM, QOL, VAS and opioid usage will be assessed before and after the procedure in both the groups. These parameters will also be evaluated at the 1-month visits.

Other relevant data will be collected through chart review. This includes patient medical, surgical history, medication history, other health conditions, demographics and exercise/physiotherapy sessions.

Primary outcomes: Improvement in shoulder range of motion (ROM) (external rotation) immediately post procedure by at least 100%

Secondary outcomes:

Sustained ROM at 1-month visit compared to pre-procedure ROM

Opioid use before after and at 1-month visit

VAS scale for an expected difference of 3 points

Quality of life questionnaire before procedure, after procedure and at 1-month visit.

Bilateral shoulder ROM improvements in subjects with bilateral procedure

Target Population: 57 adult patients will be enrolled in the Montefiore Hutchinson campus.

Power Analysis:

Assume 30% of patients in the local anesthetic group will have at least a 100% improvement in range of motion one-month post treatment. With a sample size of 32 patients in the Tenex group and 16 patients in the local

anesthetic group, the study will have 81.9% power to detect a difference of 45% in patients with at least a 100% improvement in range of motion between the Tenex group and local anesthetic group one-month post treatment using a two-sided Fisher's exact test at a 0.05 significance level.

Assume an attrition rate of 15%, 57 patients will be enrolled and randomized in a 2:1 ratio to receive either Tenex or local anesthetics.

Randomization

Block randomization was done using SPSS software by the in house statistician. Randomization is noted at the end of the document for all our patients. Please note randomization is 2:1 Tenex:LA. LA will cross over to Tenex at 1 month if the subjects desire.

Inclusion:

1. Adults >18 and <89 years
2. Established Diagnosis of Adhesive capsulitis (AC)
 - Ligament Flavum >3mm, diagnosed by US evaluation

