 - decreased shoulder ROM in external rotation and abduction (50% of unaffected side) (17)
3. Patients who have tried other conventional therapies like steroid treatments, surgical treatments, physiotherapy with little (defined by less than 20 degrees improvement in shoulder ROM – external rotation) to no improvement in the shoulder ROM

Exclusion:

1. Patients with AC but showing improvement in shoulder ROM progressively (defined by improvement in ROM > 200 external rotation or 20 degrees per week when undergoing physiotherapy)
2. Patients who are currently pregnant
3. less than 18 years old and older than 89 years old

Patient recruitment:

Patients will be identified by the PI/Co-PI and will be consented, screened and enrolled into the study by the approved research staff at the Montefiore Hutchison campus.

Informed consent:

All the subjects will be consented before enrolling into the study. A detailed informed consent is taken by the approved research staff who will explain the study in detail with regards to risks and benefits. The patient can refuse to be a part of the study at any point even after signing the consent.

Benefits:

The patients who are being recruited for this study have limited treatment options and have been suffering from frozen shoulder for years

Possible benefits include

1. Improvement in shoulder ROM
2. Improvement in VAS
3. Improvement in QOL
4. Reduced pain medication usage

Risks:

The procedure is relatively safe as the area near the CHL is relatively avascular. However, there is a risk a rupture of axillary artery. Care will be taken to ensure this does not happen by clear identification of the axillary artery by using USG.

There is a potential this procedure may not improve ROM in which case the study will be stopped, and the IRB will be informed immediately as an adverse event.

Potential for infection, although a minimally invasive procedure there will be a small incision on the skin with potential for infection. All care will be taken to perform the procedure in standard universal precautions. Post procedure the incision will be cleaned, and dressing applied. Standard wound care precautions will be given to the patients.

Study reimbursement: None

Statistical analysis:

Differences in VAS, opioid use, and QOL scores before and after the procedure will be compared using paired t-tests or Wilcoxon singed-rank tests.

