Assume 30% of patients in the local anesthetic group will have at least a 100% improvement in range of motion one-month post treatment. With a sample size of 32 patients in the Tenex group and 16 patients in the local anesthetic group, the study will have 81.9% power to detect a difference of 45% in patients with at least a 100% improvement in range of motion between the Tenex group and local anesthetic group one-month post treatment using a two-sided Fisher's exact test at a 0.05 significance level.

Assume an attrition rate of 15%, 57 patients will be enrolled and randomized in a 2:1 ratio to receive either Tenex or local anesthetics.

Data analysis:

Simple descriptive statistics will be used in analysis of the data. The main primary outcome is the improvement in shoulder ROM and we expect to improve the ROM by at least 100 percent in external rotation. Differences in VAS, pain medication use, and QOL scores before and after the procedure will be compared using paired t-tests or Wilcoxon singed-rank tests.

Data Safety

The PI will give assurances of data safety as well as the timely report of any breach. The data will be stored on a password protected encrypted computer which is located in a locked room with access only to the PI and the research staff. The data reported will be deidentified and any chances of identifying information will be minimized. In addition, the data will be stored on an password protected excel file on the above password protected computers. The identifiers will be destroyed at the end of the study i.e., 3 years from the start of the study.

Subject Safety

In addition to following the inclusion/exclusion criteria, [REDACTED] will be available on the day of the procedure. He will not be scrubbed in to any other case and will be available for immediate back up in case of a medical or surgical complication on the day of the Tenex procedure. Please note he will also be in the same building.

DSMB and DSMP

Data safety monitoring board will be managed by [name], [name] and [name] [name]. All the three above Physicians are independent researchers and practicing clinicians with expertise in managing chronic pain at Montefiore. They are not associated with the study. [name] and [name] practice in Orthopedics and [name] practices Anesthesiology and pain medicine.

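### VAS, opioid use and QOL get only before-after tests, and the primary ROM outcome has no between-arm test at its own time point, so change shared by both arms would read as benefit

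*Combined protocol and SAP*

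**What the plan says.** - **Design.** Under Study Design, both arms are measured: "Subjects shoulder ROM, QOL, VAS and opioid usage will be assessed before and after the procedure in both the groups". The same measures are repeated at the 1-month visit. The background treatment is common to both arms: "Both groups will be receiving the same anesthetic". Control patients may cross over at the 1-month visit.
- **Secondary outcomes.** The Statistical analysis section says "Differences in VAS, opioid use, and QOL scores before and after the procedure will be compared using paired t-tests or Wilcoxon singed-rank tests". Data analysis repeats it almost word for word: "Differences in VAS, pain medication use, and QOL scores before and after the procedure will be compared using paired t-tests or Wilcoxon singed-rank tests". Neither sentence names an arm or says whether the paired tests are run within each arm or on all patients together.
- **Primary outcome.** It is defined as "Improvement in shoulder range of motion (ROM) (external rotation) immediately post procedure by at least 100" per cent. Data analysis opens with "Simple descriptive statistics will be used in analysis of the data" and then states the expected improvement without a comparator.
- **The one between-arm test.** It appears in the sample-size text, printed under Power Analysis and again under Statistical analysis: a comparison "between the Tenex group and local anesthetic group one-month post treatment using a two-sided Fisher's exact test" at the 0.05 level.
- **Later ROM.** The first secondary outcome is "Sustained ROM at 1-month visit compared to pre-procedure ROM", again set against the patient's own baseline.

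**The concern.** A paired test asks whether patients changed. It does not ask whether Tenex patients changed more than controls. Both arms receive the same anesthetic, so some of the change in pain straight after the procedure is likely to be common to both. The plan itself expects control patients to improve: it assumes that 30% of them will reach the 100% ROM threshold at one month.

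Followed as written, the VAS, opioid and QOL analyses cannot show a Tenex effect. A small before-after p-value could still be reported as benefit when the arms do not differ. The primary outcome at its own time point would be described without a stated test against the randomised control.

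**Working it through.** **1. The plan's own figure.** Inputs from the sample-size text: 32 Tenex and 16 control patients, responder rates 30% + 45 points = 75% v 30%, two-sided Fisher's exact test, alpha 0.05. Summing the binomial probabilities of all outcome pairs with Fisher p ≤ 0.05 gives 0.8195, against 81.9% stated. Enrolment also reproduces: 48 / 0.85 = 56.5, rounded up to 57. The arithmetic is sound, but it concerns one-month responders.

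**2. Paired test with no device effect.** Let both arms have the same mean change m, with SD of change s. The paired t statistic in n patients is noncentral t with n − 1 degrees of freedom and noncentrality (m/s)√n. The rejection rate is P(|T| > t(0.975, n − 1)). For n = 32 the critical value is 2.040. With m = 1.0 and s = 2.5 the noncentrality is 0.4 × √32 = 2.263, and the rejection rate is 0.592.

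The documents give neither m nor s, so both are assumed:

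| Shared VAS change (points) | 0.5 | 0.75 | 1.0 | 1.5 |
|---|---|---|---|---|
| Tenex arm, n = 32, SD 2 | 27.8% | 53.8% | 78.2% | 98.4% |
| Tenex arm, n = 32, SD 2.5 | 19.5% | 37.6% | 59.2% | 90.8% |
| Tenex arm, n = 32, SD 3 | 15.0% | 27.8% | 44.7% | 78.2% |
| Arms pooled, n = 48, SD 2.5 | 27.4% | 53.0% | 77.5% | 98.3% |

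A between-arm t-test on change in the same scenarios rejects at the nominal 5% (simulated at SD 2.5 with 40,000 runs: 4.8% to 5.1%).

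**3. Setting the two arms' p-values side by side does not help.** For an identical change of 0.5 SD in both arms, the paired test is significant with probability 0.782 in 32 Tenex patients and 0.465 in 16 controls. The pattern of Tenex significant and control not then occurs with probability 0.782 × (1 − 0.465) = 0.42, purely because the arms differ in size.

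**4. What a between-arm test could do.** For a two-sample t-test at 32 v 16 the noncentrality is (δ/s) / √(1/32 + 1/16), with 46 degrees of freedom. The Secondary outcomes list an expected VAS difference of 3 points without saying whether it is within patients or between arms. Read as between arms, with s = 2.5, the noncentrality is 1.2 / 0.306 = 3.92.

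| True between-arm difference | SD 2 | SD 2.5 | SD 3 |
|---|---|---|---|
| 3 points | 99.8% | 97.0% | 89.2% |
| 2 points | 89.2% | 72.5% | 56.8% |

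**5. Primary outcome at its own time point.** The 81.9% carries over only if the one-month rates also hold immediately. With Tenex held at 75% and an assumed immediate control rate of 20%, 40% or 50%, Fisher's exact test has 95.6%, 58.8% or 33.5% power.

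**The case against.** The strongest reply is that the plan already contains a randomised comparison. The Fisher test is printed twice, once under Statistical analysis itself, and the general sentence on descriptive statistics does not withdraw it. On this view the ROM half is only a time-point mismatch. That is fair as far as it goes: a one-month ROM conclusion is protected from shared change. The outcome named as primary is not, because no test is stated where it is measured.

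Second, VAS, opioid use and QOL are secondary, and nothing says a paired p-value will be used to claim superiority. True, but the paired test is the only analysis stated for them, it is stated twice, and improvements in VAS, QOL and pain medication use are listed under Benefits.

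Third, the percentages are not type I errors of the paired test, since the patients really did change. They also rest on assumed values. Both points stand: the figures show how often a real shared change would be significant and so open to misreading as a device effect.

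Fourth, 32 and 48 are the numbers left after one-month attrition. Immediately after the procedure 38 Tenex patients could be available (57 × 2/3). At SD 2.5 the rates are then 22.5%, 43.7%, 67.1% and 95.0%, which makes the problem larger.

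Fifth, physiotherapy is a weaker example of shared change than the anesthetic. The plan only collects it from charts, and it could not explain an immediate change.

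Last, testing at two times raises a question of multiplicity. The outcome lists already make the immediate result primary and the 1-month result secondary, but the revised text should say so explicitly.

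**Conclusion.** The concern holds and must be fixed. For three secondary outcomes the stated rule produces no comparison of the randomised arms, and the primary outcome has none at its own time point. This is a wrong choice of comparison, not an omitted detail or an arithmetic error.

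For a shared VAS change of 0.5 to 1.5 points and no device effect, the Tenex before-after test would be significant in 20% to 91% of trials at SD 2.5 (15% to 78% at SD 3, 28% to 98% at SD 2), against 5% for a between-arm test. The direction does not depend on the assumed SD or shared change; the exact percentages do.

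**What to change.** In Statistical analysis and Data analysis:

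- Replace the paired tests with comparisons by randomised arm, immediately post procedure and at 1 month before any crossover. Use baseline-adjusted ANCOVA for VAS and QOL and a rank-based two-sample test for opioid use, each with an estimate and 95% confidence interval.
- State that the two-sided Fisher's exact test applies to the responder outcome immediately post procedure as the primary analysis, and at 1 month as secondary.
- Report external rotation in degrees by baseline-adjusted ANCOVA as supportive.
- Keep before-after results as description, shown by arm.
- Say whether the 3-point VAS difference is between arms, and give the assumed immediate control responder rate, since the present power statement covers one month only.

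The cost is wording: the measures are already collected in both arms at all three times. Before-after p-values are lost as headline results, and the between-arm test is weaker for small effects, with 73% power for a true 2-point VAS difference at SD 2.5 (57% at SD 3, 89% at SD 2).

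### VAS, opioid use and QOL have only a paired before/after test; the time of 'after' is undefined, most naturally the procedure day, and no test is named for the 1-month values

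*Combined protocol and SAP*

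**What the plan says.** **Assessment times.** The Study Design section says "Subjects shoulder ROM, QOL, VAS and opioid usage will be assessed before and after the procedure in both the groups", and then adds "These parameters will also be evaluated at the 1-month visits". The secondary outcomes follow the same pattern. QOL is listed as "Quality of life questionnaire before procedure, after procedure and at 1-month visit", and opioid use is listed at the same three times. The VAS outcome is given as "VAS scale for an expected difference of 3 points", with no visit attached and no statement whether the difference is within patients or between arms.

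**Tests.** The Statistical analysis section says: "Differences in VAS, opioid use, and QOL scores before and after the procedure will be compared using paired t-tests", with the Wilcoxon signed-rank test as the alternative. The Data analysis section repeats this with a broader medication term: "Differences in VAS, pain medication use, and QOL scores before and after the procedure will be compared using paired t-tests". The only other general statement is "Simple descriptive statistics will be used in analysis of the data".

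**Related design features.** The primary outcome, external rotation, is set right after the procedure. The Power Analysis uses the proportion of patients whose ROM at least doubles by one month, compared between arms with Fisher's exact test. Both arms receive the same local anesthetic. Patients in the local anesthetic arm may cross over to Tenex at the 1-month visit.

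**The concern.** A paired test takes two values per patient, and this plan collects three: before, after and 1 month. The test sentences use the words that the outcome list reserves for the first two. Read in the plan's own vocabulary, the test stops at 'after' and the 1-month value is left with descriptive statistics only.

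If 'after' is the procedure day, that is a poor choice of time for all three outcomes. Opioid use is a quantity over a period, and essentially no period has passed. A QOL score describes daily life, and the patient has not yet lived any of it with the treated shoulder. VAS can change at once, but it is then read soon after a local anesthetic given to every patient, so a fall within a patient does not show what Tenex added.

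The 1-month visit is where a treatment effect on these outcomes could appear. It is also the last assessment before the arms may merge through crossover. A trial that collects these values and tests others would have little to say about pain, opioid use or QOL.

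**Working it through.** **1. Is a figure in dispute?** No. The only sample-size figures concern ROM response at one month. They reproduce: enumerating both binomials (32 patients at 75%, 16 at 30%) with a two-sided Fisher's exact test at 0.05 gives 81.95%, against the stated 81.9%; and 48 / (1 − 0.15) = 56.5, rounded up to 57. The point rests on the text.

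**2. Collected against tested.**

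| Outcome | Before | 'After' | 1 month | Contrast in the stated test |
|---|---|---|---|---|
| Opioid use | yes | yes | yes | before vs after, paired |
| QOL | yes | yes | yes | before vs after, paired |
| VAS | yes | yes | yes (from Study Design) | before vs after, paired |

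These are three of the five secondary outcomes. The other two concern ROM.

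**3. When is 'after'?** The documents do not say. Three features point to the procedure day:
- 'After' is listed apart from the 1-month visit.
- No visit between the procedure and one month is described.
- The primary outcome already requires a measurement right after the procedure.

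In addition, the power text that directly follows the test sentence names one month explicitly, twice. The test sentence does not.

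**4. What follows under each reading.**
- *Procedure day.* The opioid and QOL contrasts compare two values with essentially no exposure time between them. The VAS contrast contains anesthetic relief.
- *Any time after the procedure.* There are two follow-up values and one paired test. Which value is tested is open and could be settled after the data are seen.

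**5. Illustration: a paired VAS test with no device effect.** Suppose both arms improve by the same amount and the within-patient change has an SD of 2.5 points. Both figures are assumptions; the documents give neither. The chance of a significant two-sided paired t-test comes from the noncentral t distribution with noncentrality (change / 2.5) × √n:

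| Shared change | n = 16 | n = 32 | n = 48 |
|---|---|---|---|
| 1 point | 32% | 59% | 77% |
| 2 points | 85% | 99% | >99% |
| 3 points | 99% | >99% | >99% |

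A significant paired result is therefore compatible with no contribution from Tenex.

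**6. Illustration: is a between-arm 1-month VAS test feasible?** Take 32 and 16 evaluable patients, treat the 3 points as a difference between arms (an assumption), and use power ≈ Φ(3 / [SD × √(1/32 + 1/16)] − 1.96), where the square root is 0.306. With an assumed SD of 3.0, this is 3 / 0.919 − 1.96 = 1.31, or 90%. Over a range of assumed SDs, power is 97% at 2.5, 90% at 3.0, 80% at 3.5 and 69% at 4.0. The calculation is not adjusted for baseline.

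**The case against.** The strongest reply is that 'before and after the procedure' is ordinary shorthand for pre- versus post-treatment. A 1-month value is also after the procedure, and opioid use and QOL at one month are named among the secondary outcomes, so the sentence may be meant to cover every follow-up. That reading is open. It does not settle the matter, because a single paired test then faces two follow-up values and the plan does not say which counts.

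A reader might infer more than the documents support:

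- *That the test is definitely a same-day one.* The documents never say so. The timing right after the procedure is attached to the primary ROM outcome alone.
- *That the opioid and QOL results are bound to be null.* This needs the procedure-day reading and also an assumption about recall periods, which are not given.
- *That anesthetic relief alone would meet the 3-point VAS expectation.* The documents give no size for that relief.
- *That the timing fault would be just as serious for VAS in a between-arm test.* Because both arms receive the same anesthetic, a between-arm contrast would largely cancel the shared relief. A floor effect could still hide a difference. For VAS the main trouble is the within-patient comparison combined with the timing.
- *That the 1-month values will go unreported.* Descriptive statistics are planned and can cover them.
- *That the trial forfeits most of its claimed benefits.* The Benefits section lists possible benefits to participants. These are not hypotheses of the trial.

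It is also fair to object that moving the paired test to one month would not be enough. A pre-to-1-month change within patients mixes any Tenex effect with natural course, regression to the mean and other care.

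**Conclusion.** The point holds in a limited form. It is certain from the text that the only test stated for these three outcomes is a paired before/after comparison, that 'after' is listed separately from the 1-month visit, and that no test is named for the 1-month values. It is a well-supported inference, not a stated fact, that 'after' means the procedure day. The statements that opioid use and QOL have had essentially no time to change, and that within-patient VAS change is confounded by the anesthetic, depend on that inference. If it is wrong, the fault that remains is an unspecified choice between two follow-up values.

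Three of the five secondary outcomes are affected. The ROM outcomes and the stated power are not. Nothing in the documents allows the effect on the results to be sized, and the figures in steps 5 and 6 of the working are illustrations under assumed SDs and changes. The plan should be changed, since the better values are already being collected.

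**What to change.** - State when the 'after' assessment takes place.
- Make the 1-month value the tested time point for VAS, opioid use and QOL, measured before any crossover at that visit.
- Compare it between the randomized arms with adjustment for the pre-procedure value, for example by analysis of covariance, in place of the paired test.
- Attach the 3-point VAS expectation to the 1-month visit and say that it refers to a difference between arms, if that is what is meant.
- Ask about opioid use over the same recall period at baseline and at one month.
- Report the 'after' values descriptively.

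The cost is wording in the outcome list and in the Statistical analysis and Data analysis sections. No visit is added. The small downside is that 1-month values are exposed to the assumed 15% attrition, which the enrollment of 57 already allows for.

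### The Data analysis section does not say whether the 100% gain in external rotation is per patient or an average, and it omits the between-arm responder test that the sample size is built on

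*Combined protocol and SAP*

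**What the plan says.** Four places bear on the point.

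- **Primary outcomes** (under Study Design): improvement in shoulder range of motion, "external rotation) immediately post procedure by at least 100"%. The line does not say whether the threshold is for each patient or for the group.
- **Power Analysis**, repeated in full under **Statistical analysis**: "Assume 30% of patients in the local anesthetic group will have at least a 100% improvement in range of motion one-month post treatment". The trial is sized "to detect a difference of 45% in patients with at least a 100% improvement in range of motion" between Tenex and local anesthetic, using a two-sided Fisher's exact test at 0.05 with 32 and 16 patients, for 81.9% power.
- **Data analysis**, on method: "Simple descriptive statistics will be used in analysis of the data". On the primary outcome: "we expect to improve the ROM by at least 100 percent in external rotation".
- **Data analysis**, on tests: "Differences in VAS, pain medication use, and QOL scores before and after the procedure will be compared using paired t-tests" or the Wilcoxon alternative. These are before-and-after tests and do not cover range of motion.

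**The concern.** The power statement counts patients who each reach a threshold and compares that count between randomised arms. The Data analysis sentence gives an expected size of gain, with no count, comparator or test. An average percentage gain and a proportion of patients past a threshold are different quantities. Percentage gains divide by baseline, so a few patients with very low baselines can pull a mean past 100% while most patients fall well short. Conversely, many patients just past 100% can coexist with a mean below it.

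At stake is what gets reported as the primary result. Followed literally, the section would allow a descriptive gain in the Tenex arm alone to be presented as the primary finding, even if the randomised comparison the trial was sized for is negative.

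**Working it through.** **Inputs from the documents.** Responder rate 30% on local anesthetic; difference 45 points, so 75% on Tenex; 32 v 16 evaluable; two-sided Fisher's exact test at 0.05; attrition 15%; 57 enrolled at 2:1, which is 38 v 19. No SD and no baseline external rotation are given.

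**1. Reproduce the plan's figure.** Power is the sum, over all 33 × 17 possible tables, of Binomial(32, 0.75) × Binomial(16, 0.30) probabilities for tables with Fisher p ≤ 0.05. The result is 81.95%, against 81.9% stated. Attrition: 48 / (1 − 0.15) = 56.5, rounded up to 57, as stated. The design is therefore a between-arm comparison of responder proportions.

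**2. Can an average gain and the responder comparison disagree?** Illustrative data at 32 v 16, with 5/16 (31%) responders on local anesthetic, close to the planned 30%:

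- *Average meets 100%, comparison fails.* On Tenex, 12 patients gain 250% and 20 gain 20%. Mean = (12 × 250 + 20 × 20) / 32 = 3400 / 32 = 106%. Responders 12/32 = 37.5%. Fisher p = 0.76.
- *Average misses 100%, comparison succeeds.* On Tenex, 24 patients gain 105% and 8 gain nothing. Mean = (24 × 105) / 32 = 2520 / 32 = 79%. Responders 24/32 = 75%. Fisher p = 0.005.

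Against 5/16, at least 21/32 Tenex responders (66%) are needed for p ≤ 0.05. These examples need no distributional assumption. They show that disagreement is possible, not how likely it is.

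**3. How often might it happen?** This needs an assumption. Let R = post/pre external rotation, with ln R normal and SD *s* between 0.4 and 1.0. To give a responder rate *p*, set the mean of ln R to μ = ln 2 + *s* × Φ⁻¹(*p*). The true mean gain is exp(μ + *s*²/2) − 1.

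For *p* = 40%, Φ⁻¹(0.40) = −0.253:

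- *s* = 0.4: μ = 0.693 − 0.101 = 0.592; mean gain = exp(0.592 + 0.080) − 1 = 96%.
- *s* = 1.0: μ = 0.693 − 0.253 = 0.440; mean gain = exp(0.440 + 0.500) − 1 = 156%.

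In 20,000 simulated trials per setting at 38 v 19, with 40% v 30% responders, the share in which the Tenex summary reaches 100% while Fisher is non-significant is:

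- using the mean: about 30–78%, rising with *s*;
- using the median: about 7%, whatever *s* is, because a median gain of 100% essentially requires half the patients to be responders.

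**4. How much of this is low power?** Exact Fisher power at 40% v 30% and 38 v 19 is about 9%, so the test is non-significant in about 91% of such trials whatever descriptive summary is placed beside it.

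**The case against.** The strongest reply is that the documents already contain the responder endpoint. The power paragraph appears again under Statistical analysis, directly before Data analysis, and names the measure, the two arms, the test and the significance level. The Primary outcomes line uses the same 100% threshold. The Data analysis sentence says only what the team expects; it may be shorthand for that endpoint, and it sets no explicit success criterion.

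Much of this stands. A reader might infer that the section adopts a group mean as the primary benchmark. The documents do not support that: neither word occurs there, and an average is only one possible reading, though a realistic one, since the Background reports the seven earlier patients by their average gain (40 degrees in external rotation).

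A reader might also take the simulated frequencies as the trial's error rates. They are not. They depend on choosing the mean over the median, on an assumed spread, and on a difference at which Fisher power is very low. The widest spread is also hard to believe: at *s* = 1.0 with 40% responders, Φ(−0.440) = 33% of patients would end with less external rotation than they started with. At the control rate of 30%, μ = 0.693 − 0.524 = 0.169 and the share is Φ(−0.169) = 43%.

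What the reply does not remove is the gap in the text. The repeated paragraph is worded as an assumption and a power figure; no sentence makes that comparison the primary analysis. The section that does describe the analysis prescribes descriptive statistics and names tests only for other outcomes.

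**Conclusion.** The point holds as an ambiguity with consequences. The plan is sized for one quantity, and its analysis section describes the primary outcome in words that do not identify that quantity, the comparison or the test. The power arithmetic itself is correct.

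That an average gain and the responder comparison can conflict in both directions is established by the examples at the plan's own evaluable numbers. The frequency of conflict is not established. The range from about 7% (median) to about 30–78% (mean), at 40% v 30% responders, rests on the lognormal assumption and a spread the documents do not give, and part of it reflects low power at that difference. The case for changing the text rests on the missing specification and does not need any of these frequencies.

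**What to change.** In Data analysis, replace the first two sentences (the one prescribing descriptive statistics and the one on the primary outcome) with:

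> The primary outcome is the proportion of patients whose external rotation improves by at least 100% from baseline, compared between the randomised Tenex and local anesthetic groups by two-sided Fisher's exact test at 0.05, as in the power statement. Mean or median percentage improvement is descriptive and is not a criterion of success. Other data are summarised descriptively.

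The sentence on paired tests for VAS, medication use and QOL can stay after it. In the Primary outcomes line, state that the 100% threshold applies to each patient. Reconcile the time point there (immediately post procedure) with the one in the power statement (one month), so that a single time is named throughout. The power text should also specify external rotation, since it refers only to range of motion.

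The cost is a few sentences, with no change to data collection or patient numbers. The downside for the sponsor is that an average gain above 100% can no longer be presented as the primary result.
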